#### 7.3. Unscheduled Visits

If, during the investigation, a subject requires an unscheduled visit to the clinical site, the following information will be collected as appropriate:

- Chief complaint prompting the visit. If the reason is an adverse event, the applicable eCRF for the adverse event must be completed and subject record completed as appropriate.
- Date and time of the visit and all procedures completed at the unscheduled visit.
- Review of adverse event and concomitant medications.
- Slit lamp findings (using the Slit Lamp Classification Scale).

If the Investigator withdraws a subject from the study, the final study visit case report forms must be completed indicating the reason(s) why the subject was withdrawn. The subject record must be completed documenting the date and primary reason for withdrawal and the study CRA notified.

Any ocular and non-ocular Adverse Events that are ongoing at the time of the study visit will be followed by the Investigator, within licensure, until they have resolved, returned to pre-treatment status, stabilized, or been satisfactorily explained. If further treatment i.e., beyond licensure is required, the subject will be referred to the appropriate health care provider.

The following information will be collected during an unscheduled visit as appropriate.

Unscheduled Visit					
Step	Procedure	Details			
U.1	Chief Complaints	Record the subject's chief complaints for reasons for the unscheduled visit.			

Unscheduled Visit				
Step	Procedure	Details		
U.2	Adverse Events and Concomitant Medications Review	Review any changes to the subject's medical history or concomitant medications from the previous study visit. Record any changes, and any adverse events.	-	
U.3	Entrance VA	Record the entrance distance visual acuity (OD, OS and OU) to the nearest letter.		
U.4	Subjective Sphero- cylindrical Refraction	Perform bare-eye subjective spherocylindrical refraction with a phoropter (adopt the maximum plus to maximum visual acuity (MPMVA) approach and use the duo-chrome test for binocular balancing) and record the best corrected distance visual acuity to the nearest letter (OD, OS, and OU).		
U.5	Slit Lamp Biomicroscopy	FDA Slit Lamp Classification Scale will be used to grade the findings. If the clearance of the fluorescein needs to be expedited, preservative-free rewetting drops may be instilled.		
U.6	Exit Visual Acuity	Record the subject's exit distance visual acuity (OD, OS, and OU) to the nearest letter.	A.	

#### 7.4. Laboratory Procedures

Not Applicable

#### 8. SUBJECTS COMPLETION/WITHDRAWAL

#### 8.1. Completion Criteria

Subjects are considered to have completed the study if they:

- provided informed consent and/or assent;
- they are eligible;
- Completed all study visits;
  - Have not withdrawn/discontinued from the study for any reason described in Section 8.2

#### 8.2. Withdrawal/Discontinuation from the Study

A subject will be withdrawn from the study for any of the following reasons:

- · Subject death during the study period
- Subject withdrawal of consent and/or assent
- Subject not compliant to protocol

- Subject lost to follow-up
- Subject no longer meets eligibility criteria (eg the subject becomes pregnant)
- Subject develops significant or serious adverse events causing discontinuation of study lens wear
- Subjects who have experienced a Corneal Infiltrative Event (CIE)
- Investigator's clinical judgment regarding the subject safety reasons (that it is in the best interest of the subject to stop treatment)

For discontinued subjects, the Investigator will:

- Complete the current visit (scheduled or unscheduled)
- Complete the Final Evaluation, indicating the reason that the subject was discontinued from the study
- Record the spherocylindrical refraction with best corrected distance visual acuity, as appropriate
- Collect used test article(s) (worn or brought to the visit) from the subject and discard them, unless otherwise stated in Section 7.2
- Collect all unused test article(s) from the subject

An additional subject may be enrolled if a subject discontinues from the study prematurely.

In cases where a subject is lost to follow-up, every possible effort must be made to contact the subject and determine the reason for discontinuation/withdrawal. The measures taken to follow up must be documented including two written attempts and a certified letter (or equivalent) as the final attempt.

#### 9. PRE-STUDY AND CONCOMITANT INTERVENTION/MEDICATION

Concomitant medications will be documented during screening and updated during the study. Disallowed medications for this study include: None

Concomitant therapies that are disallowed include: None

#### 9.1. Systemic Medications

Due to the non-dispensing, single visit nature of the study and endpoints being assessed, systemic medications will be allowed provided they did not interfere with contact lens wear, which will be at the discretion of the investigator.

Disallowed systemic medications - Not applicable

#### 10. DEVIATIONS FROM THE PROTOCOL

Investigator will notify study sponsor upon identification of a protocol deviation. Protocol deviations must be reported to the sponsor within 24 hours after discovery of the protocol

deviation. The Investigator will report deviations per IRB/IEC requirements. All deviations will be tracked and corrective actions implemented as appropriate.

If it becomes necessary for the Investigator to implement a deviation in order to eliminate an immediate hazard to the trial subject, the Investigator may implement the deviation immediately without notification to the sponsor. Within 24 hours after the implemented deviation, the Investigator must notify and provide the rationale to the Sponsor and, as required, the IEC/IRB.

If the deviation potentially impacts the safety of patient or changes the technical integrity of the study then it must be reported to IEC/IRB. This is a "Major Deviation".

Minor deviations have no substantive effect on patient safety or technical integrity of the study. They are often logistical in nature. The informed consent must also not be contradicted by the deviation.

Protocol waivers are prohibited

#### 11. STUDY TERMINATION

The occurrence of one or more Unanticipated Serious Adverse Device Effect (USADE), or any SAE where the relationship to study agent cannot be ruled out, may result in stopping further dispensing of test article. In the event of a USADE or SAE, the Sponsor may unmask the treatment regimen for the subject(s) and will discuss this with the Investigator before any further subjects are enrolled.

The Sponsor will determine when a study will be stopped. The Principal Investigator always has the discretion to initiate stopping the study based on patient safety or if information indicates the study's results are compromised.

JJVC reserves the right to terminate the study at any time for any reason. Additionally, the IEC/IRB reserves the right to terminate the study if an unreasonable risk is determined. The study can be terminated by the Principal Investigator at the individual clinical site due to specific clinical observations, if in their opinion, after a discussion with JJVC, it is determined that it would be unwise to continue at the clinical site.

JJVC (and the IEC/IRB and DMC, if applicable) will evaluate all adverse events. If it is determined that an adverse event presents an unreasonable risk, the investigation, or that part of the investigation presenting the risk, will be terminated as soon as possible.

Should the study be terminated (either prematurely or as scheduled), the Investigator will notify the IEC/IRB and Regulatory Authority as required by local regulatory requirements.

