	tarsal abnormalities, bulbar injection, corneal edema,
	corneal vascularization, corneal staining, or any other
	abnormalities of the cornea which would
Disallary 1	contraindicate contact lens wear.
Disallowed Medications/Interventions	None
Measurements and	logMAD vigual aquity long fit aggregation to aggregate long fit
Procedures	logMAR visual acuity, lens fit assessment, cosmetic lens fit
Tiocedules	assessment/hula hoop assessment, and safety parameters (slit lamp findings, entrance/exit visual acuity).
Microbiology or Other	None
Laboratory Testing	TYORC
Laboratory resumg	

Study Termination	The occurrence of one or more Unanticipated Adverse
	Device Effect (UADE), or any SAE where relationship to
	study agent cannot be ruled out, will result in stopping
	further dispensing investigational product. In the event of a
	UADE or SAE, the Sponsor Medical Monitor may unmask
	the treatment regimen of subject(s) and may discuss this with
	the Principal Investigator before any further subjects are
	enrolled.
Ancillary Supplies/ Study-	Tears Naturale re-wetting drops, FluStrips fluorescein strips,
Specific Materials	Bausch & Lomb Sensitive Eyes plus Saline, or alternative
	products approved by the Sponsor.
Principal Investigator(s)	A full list of Principal Investigators, clinical sites, and
and Study	institutions is kept separately from the Study Protocol and is
Institution(s)/Site(s)	included in the study Trial Master File.

Figure 1: Study Flowchart

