#### 4.3. Enrollment Target and Study Duration

Approximately 40 subjects ages 18 to 39 years (inclusive) who are habitual soft contact lens wearers will be enrolled in this single-visit clinical study with the goal of 34 subjects to complete. While both male and female patients are eligible to participate, we will aim to enroll female subjects ages 18-29 years.

Enrollment is defined as execution of the informed consent form.

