#### 5.3. Procedures for Maintaining and Breaking the Masking

The Clinical Supply Unit will generate a unique code for all study lenses. Marketed products and investigational lenses will have nearly identical labels, differing only in the product specifications and lens code, to maintain masking. Subjects will be dispensed lenses by the lens code in accordance with the randomization scheme provided by the study statistician.

The test articles mask shall not be broken unless information concerning the lens type is necessary for the urgent medical treatment of a subject. The Sponsor must be notified before the mask is broken.

When dispensing test articles, the following steps should be followed to maintain randomization codes:

- Investigator or designee (documented on the Delegation Log) will consult the lens fitting schedule/randomization scheme to obtain the test article assignment for that subject prior to dispensing.
- Investigator or designee will record the subject's number on the appropriate line of the randomization scheme.
- 3. Investigator or designee will pull the appropriate test articles from the study supply. All test articles that are opened, whether dispensed (placed/fit on eye or dispensed outside the clinical site) or not, must be recorded on the Test Article Accountability Log in the "Dispensed" section.

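### The synopsis makes a safety stop on dispensing mandatory and Section 11 makes it optional; the two texts may also differ on which lenses are stopped

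*Combined protocol and SAP*

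**What the plan says.** The Study Termination row of the synopsis names as its trigger one or more UADEs, or any SAE whose relationship to "study agent cannot be ruled out, will result in stopping" further dispensing. What is stopped there is the investigational product. After such an event the Sponsor Medical Monitor may unmask "the treatment regimen of subject(s) and may discuss this with" the Principal Investigator ahead of further enrolment.

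Section 11 (Study Termination) starts from one or more unanticipated serious adverse device effects (USADE), or the same SAE criterion, and says that this "may result in stopping further dispensing of test article". Here the Sponsor may unmask "and will discuss this with the Investigator before any further subjects are enrolled".

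Section 11 then gives the sponsor the decision on when a study is stopped and lets the Principal Investigator initiate stopping on safety grounds. If an adverse event is determined to be an unreasonable risk, the investigation, or the part of it that carries the risk, "will be terminated as soon as possible". Section 8.2 lists among the reasons for withdrawing a subject: "Subject develops significant or serious adverse events causing discontinuation of study lens wear".

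**The concern.** A stopping rule should tell the site and the sponsor in advance what follows a serious event. Here the answer depends on which page is read.

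Take one subject who develops iritis, which Section 13.1 lists as an ocular SAE, and suppose it is graded possibly related. By the definition in Section 13.2.1 the causal link is then not excluded, so the SAE part of the trigger is met in both texts. Under the synopsis the Test lens may not be fitted to anyone else. Under Section 11 fitting may continue.

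Section 10 prohibits waivers. It also treats a deviation that could affect subject safety as major and reportable to the IEC/IRB. So the same act, fitting the next subject, is either permitted conduct or a possible major deviation. Those affected are the subjects who have yet to wear the Test lens, including anyone between the two periods when the event is found.

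**Working it through.** No arithmetic applies. The check is to set the two texts side by side and see whether anything else in the protocol reconciles them.

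| Element | Synopsis, Study Termination | Section 11 |
|---|---|---|
| Device-effect trigger | UADE | USADE |
| SAE trigger | Any SAE whose link to the study agent is not excluded | The same |
| Force of the stop | Mandatory | Optional |
| What is stopped | Investigational product | Test article |
| Discussion with investigator | Optional | Required |

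1. *Is the trigger the same?* The SAE limb is. The device-effect limb uses two labels, but the UADE definition in Section 13.1 already confines it to serious effects or problems, and the UADE heading in Section 13.4.1 puts the word serious in brackets. USADE appears in the abbreviation list and in Section 11 and has no definition of its own. The triggers are essentially the same.

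2. *Does the rule have any effect in a study described as non-dispensing?* Yes. Section 5.3 requires every opened lens to be logged, "whether dispensed (placed/fit on eye or dispensed outside the clinical site) or not". A lens put on the eye at the site therefore counts as dispensed.

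3. *Is the scope the same?* It may not be. The Test Articles row of the synopsis puts the etafilcon A lens with cosmetic pattern under investigational products and the Control under approved products, and Section 1.1 draws the same distinction. Table 1 (Section 6.1), headed Test Articles, contains both. On these usages the mandatory stop covers the Test lens only, while the optional one could reach both lenses.

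4. *Does another provision settle the conflict?* Nothing supplied says whether the synopsis or the body prevails. The change history for version 2.0 lists step numbering, labelling protocol numbers and the COVID appendix, none of which concerns this rule.

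5. *How far does the unreasonable-risk clause go?* It compels termination, and can be limited to one part of the investigation, but only after a determination has been made. The synopsis rule acts on the event itself. The conflict is therefore confined to a qualifying event, in practice a possibly related SAE, that is not judged an unreasonable risk or has not yet been judged.

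**The case against.** The strongest reply is that a synopsis only summarises, that Section 11 is the full rule, and that it leaves stopping to the sponsor. In a single-visit fitting study, halting all fitting comes close to halting the study, so the sentence giving the sponsor that decision arguably covers dispensing too. The duty to terminate for an unreasonable risk, in whole or in part, then handles the cases that matter.

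Part of this stands. The unreasonable-risk clause narrows the conflict, as shown above. The affected subject is withdrawn anyway when a serious event ends lens wear, and stopping on every trigger satisfies both texts. What does not stand is the claim that nothing is left. A summary may shorten a rule, but this one states a stricter rule and nothing subordinates it. Reading the sponsor's decision to include fitting supports the optional version without removing the mandatory one.

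A reader might also infer more than the documents support:

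- *That Section 11 leaves the sponsor free to carry on after any serious event.* It does not, given the termination duty and the investigator's power to initiate stopping.
- *That the mandatory stop already covers the Control.* The synopsis wording does not establish this.
- *That the number of exposed subjects or lenses can be stated.* It cannot. Steps 1.16 and 1.28 allow two power modifications per eye in each period, damaged lenses are replaced, the Control may be out of scope, and some subjects may be between periods.
- *That the enrolment anchor is part of the conflict.* Section 4.3 states: "Enrollment is defined as execution of the informed consent form". A subject who has already consented could therefore be fitted before the discussion takes place, but both texts use the same anchor, so they do not differ here.

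**Conclusion.** The inconsistency is real and minor. The synopsis and Section 11 give the same safety trigger a mandatory and an optional consequence, may differ on which lenses are covered, and differ on whether discussion with the investigator is required. No precedence is stated.

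The practical risk is low. Each lens type is worn for about 90 minutes (Section 1.2), and Section 1.5 reports no serious or unanticipated adverse events in previous studies of the etafilcon A with PVP cosmetic lenses. The wording touches neither the primary analysis, nor the type I error rate, nor the sample size.

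The conclusion rests on two readings: that UADE and USADE denote the same kind of event, which the Section 13.1 definition supports, and that fitting counts as dispensing, which Section 5.3 supports. The difference in product scope is less certain, because it depends on the synopsis using its product labels consistently.

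**What to change.** State one rule in the synopsis and in Section 11:

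- **Trigger:** a UADE as defined in Section 13.1, or any SAE whose relationship to the study agent is not excluded. Use the single term UADE and remove USADE from Section 11 and the abbreviation list.
- **Consequence:** further dispensing of the investigational (Test) lens stops. Name the Control as well if the sponsor means test article to cover both. On the product labels in the synopsis, neither text currently mandates stopping the Control, so that should be an explicit choice.
- **Discussion:** the sponsor may unmask, and must discuss the matter with the investigator before enrolling anyone else.

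This complies with both current texts. The downside is that the sponsor loses the discretion to keep fitting while a single possibly related SAE is reviewed. Because each subject wears both lenses, stopping the Test lens in effect pauses the study and could delay reaching 34 completers.

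If the sponsor prefers discretion, the synopsis can be brought into line with Section 11 instead. That removes a mandatory stop, so the sponsor would have to decide whether the revision increases subject risk and needs IEC/IRB approval before it is implemented (Section 18.3).

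Either route is a wording change, sent to the IEC/IRB where appropriate, with no extra data, staff or subjects. Enrolment lasts up to 3 weeks, so the change should be made before the first subject is enrolled; failing that, sites need a written clarification of which rule applies.

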## 12. PROCEDURE FOR HANDLING PRODUCT QUALITY COMPLAINTS

A Product Quality Complaint (PQC) refers to any written, electronic, or oral communication that alleges deficiencies related to the identity, quality, durability, reliability, safety, effectiveness or performance of test articles after they have been released for clinical trial use.

Potential complaints may come from a variety of sources including but not limited to subjects, clinical research associates (CRA), clinical operations managers (COM), medical monitors, and site personnel, etc. The following are not considered product quality complaints:

- Subject satisfaction inquiries reported via "Subjective Questionnaires" and "Patient Reported Outcomes (PRO)."
- Clinical test articles that are stored improperly or damaged after receipt at the investigational site.
- Lens replacements that occur due to drops/fall-outs.
- Damage deemed by clinicians or clinical staff to be caused by handling by the user, and not indicative of a quality deficiency (i.e. tears, rips, etc.), only in situations where there is no deficiency alleged by the subject.

Within 24 hours of site personnel becoming aware that a PQC has occurred, the PQC must be recorded in the EDC system, which will trigger an automatic email notification to the appropriate COM/CRA and Clinical QA representative. In cases where the EDC system in use is not configured to send automatic notifications or when an EDC system is not used, the COM/CRA is responsible for notifying Clinical QA upon discovery that a PQC has occurred.

Upon receipt of the EDC notification, the COM/CRA will contact the study site to collect additional information which will include:

- Date the complaint was received/recorded in the EDC System (Date of Sponsor Awareness).
- Who received the complaint.
- Study number.
- Clinical site information (contact name, site ID, telephone number).
- Lot number(s).
- Unique Subject Identifier(s).
- Indication of who first observed complaint (site personnel or subject).
- OD/OS indication, along with whether the lens was inserted.
- Any related AE number if applicable.
- Detailed complaint description (scheduled/unscheduled visit, wear time, symptoms, resolution of symptoms, etc.).
- Eye Care Provider objective (slit lamp) findings if applicable.
- Confirmation of product availability for return (and tracking information, if available), or rationale if product is not available for return (Refer to for test article return instructions).

Once a complaint is received, it will be assessed by the COM, CRA, or trained site personnel to determine if it is an Adverse Event/Serious Adverse Event (AE/SAE). If the complaint

results in an AE/SAE, the COM/CRA, or trained site personnel will follow Section 13 of this protocol. If the AE/SAE was potentially the result of a product quality related deficiency, these procedures also applies and will be executed in parallel.

In some cases, a PQC form may be generated in EDC by the site in error. In this event, the PQC forms will be marked "Intentionally Left Blank" or "ILB". Justification for ILB must be documented.

#### 13. ADVERSE EVENTS

#### 13.1. Definitions and Classifications

**Adverse Event (AE)** – An AE is "any untoward medical occurrence, unintended disease or injury, or untoward clinical signs (including abnormal laboratory findings) in subjects, users or other persons, whether or not related to the investigational medical device. This definition includes events related to the investigational medical device or the comparator, and to the procedures involved. For users or other persons, this definition is restricted to events related to investigational medical devices

An AE includes any condition (including a pre-existing condition) that:

- 1. Was not present prior to the study, but appeared or reappeared following initiation of the study.
- 2. Was present prior to the study, but worsened during the study. This would include any condition resulting from concomitant illnesses, reactions to concomitant medications, or progression of disease states.
- 3. Pregnancy must be documented as an adverse event and must be reported to the clinical monitor and to the Sponsor immediately upon learning of the event.

**Serious Adverse Event (SAE)** – An SAE is any adverse event that led to any of the following:

- Death
- Serious deterioration in the health of the subject that resulted in any of the following:
- Life-threatening illness or injury
- Permanent or persistent impairment of a body structure or a body function
- Hospitalization or prolongation of patient hospitalization
- Medical or surgical intervention to prevent life-threatening illness or injury or permanent impairment to a body structure or a body function.
- Chronic disease
- Fetal distress, fetal death or a congenital physical or mental impairment of birth defect.

Diagnoses and conditions that are considered Ocular Serious Adverse Events include, but not limited to:

- Microbial Keratitis (MK)
- Iritis (including cells in the anterior chamber)
- Permanent decrease in best spectacle corrected visual acuity equivalent to 2 acuity lines or greater

- Central Corneal Opacity
- Central Corneal Neovascularization
- Uveitis
- Endophthalmitis
- Hypopyon
- Hyphemia
- Penetration of Bowman's Membrane
- Persistent Epithelial Defect
- Limbal cell Damage leading to Conjunctivalization

**Significant Adverse Events** – are defined as events that are symptomatic and warrant discontinuation (temporary or permanent) of the contact lens wear

Diagnoses and conditions that are considered Ocular Significant Adverse Events include, but not limited to the following:

- Contact Lens Induced Peripheral Ulcer (CLPU)
- Significant Infiltrative Events (SIE)
- Superior Epithelial Arcuate Lesions (SEALs)
- Any Temporary Loss of > 2 Lines of BSCVA
- Other grade 3 or higher corneal findings, such as abrasions or edema
- Non-contact lens related corneal events e.g. Epidemic Keratoconjunctivitis (EKC)
- Asymptomatic Corneal Scar
- Any corneal event which necessitates temporary lens discontinuation > 2 weeks

**Non-Significant Adverse Events** – are defined as those events that are usually asymptomatic and usually do not warrant discontinuation of contact lens wear but may cause a reduction in wear time. However, the Investigator may choose to prescribe treatment as a precautionary measure.

Diagnoses and conditions that are considered Ocular Non-Significant Adverse Events include, but not limited to the following:

- Non-significant Infiltrative Event (NSIE)
- Contact Lens Papillary Conjunctivitis (CLPC)
- Superficial Punctate Keratitis (SPK)
- Conjunctivitis: Bacterial, Viral, Allergic
- Blepharitis
- Meibomianitis
- Contact Dermatitis
- Localized Allergic Reactions
- Any corneal event not explicitly defined as serious or significant adverse event, which necessitates temporary lens discontinuation < 2 weeks

**Adverse Device Effect (ADE)** – An ADE is an "adverse event related to the use of an investigational medical device.

**NOTE 1:** to entry: This definition includes adverse events resulting from insufficient or inadequate instructions for use, deployment, implantation, installation, or operation, or any malfunction of the investigational medical device.

**NOTE 2** to entry: This definition includes any event resulting from use error or from intentional misuse of the investigational medical device."

Unanticipated Adverse Device Effect (UADE) – Any serious adverse effect on health or safety or any life-threatening problem or death caused by, or associated with, the test article, if that effect, problem, or death was not previously identified in nature, severity, or degree of incidence in the investigational plan, Investigator's Brochure or protocol, or any other unanticipated serious problem associated with the test article that relates to the rights, safety and welfare of subjects.

